### 1.9.2 Methodology

This is a Phase 1, multicenter, open-label, dose-escalation study in hospitalized, bleeding, and thrombocytopenic patients. Patients with modified WHO Grade 1 (see note following Table 1. Cohort Assignment) or Grade 2 bleeding due to hematology/oncology diseases or bone marrow aplasia secondary to cancer chemo/radiotherapy will be enrolled on study and treated with allogeneic Thrombosomes (See

Appendix A- Modified WHO Bleeding Score). Patients with WHO Grade 0, 3, or 4 bleeding do not meet eligibility criteria for enrollment. The protocol will require three cohorts of patients consisting of 8 patients in each cohort for a total of 24 patients (See Table 1. Cohort Assignment).

Table 1. Cohort Assignment				
Cohort	1	2	3	Total
	n	n	n	n
WHO Grade 1*or 2	8	8	8	24

Note: \*Only a subset of patients with Grade 1 bleeding who have either epistaxis, hematuria, oral petechiae, oropharyngeal bleeding, or bleeding at invasive or other wound sites.

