All enrolled patients with active bleeding of modified WHO Grade 1 (subset of patients with either epistaxis, hematuria, oral petechiae, oropharyngeal bleeding, or bleeding at invasive or other wound sites) or Grade 2 bleeding will receive Thrombosomes. Grades 0, 3, or 4 bleeding are not inclusion criteria for enrollment. Active bleeding is defined as to occur within 4 days of infusion. If the patient progresses to grade 3 or 4 bleeding during that time, they will be excluded from the study and will not be infused. Doses will be adjusted per weight of each patient. The starting dose for patients in Cohort 1 will be approximately 5 ml of Thrombosomes or approximately  $9.45 \times 10^7$  particles/kg or 165 TGPU per kg by IV infusion. The dose for patients in Cohort 2 will be approximately 10 ml of Thrombosomes or approximately  $1.89 \times 10^8$  particles/kg or 330 TGPU per kg by IV infusion. The dose for patients in Cohort 3 will be one dose of approximately 20 ml of Thrombosomes or approximately  $3.78 \times 10^8$  particles/kg or 660 TGPU per kg by IV infusion. See Table 2.

Pre-infusion, infusion (Day 1), and post-infusion follow up through Day 30 (+2 days) will be performed as outlined in *Table 4* below. Patients require observation at a minimum through the completion of Visit 4 (6 hours post-infusion). Patients may be admitted and observed overnight at the discretion of the PI. If the subject is an in-patient on Days 3-5, he/she should be assessed and samples collected as described in Table 4.

All patients in each cohort will be evaluated for any signs of AEs, serious adverse events (SAEs) and serious adverse drug reactions (SADRs) after infusion.

Patient infusions cannot occur on the same day. Once an enrolled patient has been infused, he/she must reach Day 4 without a suspension or stopping rule (1.9.8 Stopping Rules and Procedures for Study) event being reported prior to a subsequent patient being infused. In addition, there will be at least a two-week interval between cohorts to allow an independent Data Monitoring Committee (DMC) to review all patients' accumulated safety data after visit Day 6 from Cohort 1 and then again after the last patient from Cohort 2 has completed visit Day 6 in order to recommend whether the study should advance to the next cohort. Refer to Appendix B- Flow Diagram of Study Events.

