### ***1.9.3 Assessment of Bleeding: Using WHO Bleeding Score***

Use of the WHO (World Health Organization) Bleeding Assessment will provide a standardized approach, across multiple clinical sites, in order to determine study eligibility, for assessing a patient's bleeding during the clinical trial, and for assessing the effect of Thrombosomes (if any) on bleeding. Study personnel conducting the assessment will be trained on the assessment and will be authorized by the PI to perform the assessment. This authorization will be documented on the Authorities and Responsibilities Log. The location of bleeding for all bleeding sites will be assessed by WHO grade during study at screening, (re-screening, if applicable) baseline, 1 hour, 6 hours, 24 hours post-infusion and 6 days post-infusion. In some instances, a bleeding site may not be able to be reassessed post-infusion due to the need for an invasive procedure or other procedure that would add additional risk for the subject. The protocol does not require subjects to undergo medically unnecessary procedures (or risks) only in order to perform post-infusion WHO bleeding assessments. Subjects who are transfused with red cells to treat anemia due to their underlying disease (and not because of bleeding) will not be assessed as having WHO grade 3 bleeding. Anemia from underlying disease will be designated if there is evidence of bone marrow suppression indicated by at least two of the following: leukopenia, thrombocytopenia, or reticulocytopenia; and absence of WHO grade 2 bleeding in the prior 24 hours. For designation of WHO grade 3 bleeding, red cell transfusion must be specifically related to treatment of bleeding within 24 hours of onset of bleeding. (see Table 4. Schedule of Events for timing of WHO bleeding assessments). The same person must perform assessment of pre-infusion and 1-hour post-infusion time points.

To assess bleeding and determine the WHO Bleeding Score, the patient will be interviewed, a physical examination will be performed, and the patient's chart will be reviewed. The WHO Bleeding Score will be determined using Appendix A- Modified WHO Bleeding Score.

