### **1.16 Data Analysis**

Separate data summaries will be prepared for each cohort:

- Demographic and medical history data will be summarized. For quantitative variables, summaries will include the sample size, mean, median, standard deviation, minimum, and maximum. For qualitative variables summaries include the number and percent of patients for each outcome.
- Exploratory analyses will include the observed response and the change from baseline to each of the post-infusion time points for each of the laboratory tests (hematology, coagulation, platelet and chemistry). Additionally, summaries of the number and percent of patients with both a change of  $>5\%$  from baseline and whose results are outside of reference ranges will be displayed. For quantitative variables summaries of the observed response and the change from baseline to each of the post-baseline time points will include the sample size, mean, median, standard deviation, minimum, and maximum. Additionally, for the change from baseline summaries, the statistical significance will be determined using either a t-test or the Wilcoxon Signed Rank test, as appropriate. Summaries for qualitative variables will include the number and percent of patients for each outcome.
- Incidence of AEs and SAEs per patient and by body system will be summarized showing the number and percent of patients for each outcome. Summaries will also be prepared by severity and relationship to treatment.
- Summaries of vital signs and clinical data including WHO bleeding scores will include the observed response and the change from baseline to each of the post-infusion time points for each of the variables. For quantitative variables summaries of the observed response and the change from baseline to each of the post-baseline time points will include the sample size, mean, median, standard deviation, minimum, and maximum. Additionally, for the change from baseline summaries, the statistical significance will be determined using either a t-test or the Wilcoxon Signed Rank test, as appropriate. Summaries for qualitative variables will include the number and percent of patients for each outcome.

A statistical analysis plan will be developed as part of the data analysis plan.

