## Appendix A- Modified WHO Bleeding Score

(Adapted from Supplement from Slichter SJ, Kaufman RM, Assmann SF, et al. Dose of prophylactic transfusions and prevention of hemorrhage. N Engl J Med 2010;362:600-13)

	Grade 1	Grade 2	Grade 3
Oral and nasal	
 
Oropharyngeal bleeding – total duration of all episodes in previous 24 hours <math>\leq</math> 30 minutes*
 
Petechiae of oral mucosa
 
Epistaxis – total duration of all episodes in previous 24 hours <math>\leq</math> 30 minutes*
 
	
 
Oropharyngeal bleeding – total duration of all episodes in previous 24 hours <math>></math> 30 minutes*
 
Epistaxis – total duration of all episodes in previous 24 hours <math>></math> 30 minutes*
 
	
 
Any bleeding requiring RBC transfusion over routine transfusion needs**
 

Skin, soft tissue, musculoskeletal	
 
Petechiae of skin
 
Purpura <math>\leq</math> 1 inch diameter
 
One or more spontaneous hematomas in the soft tissue or muscle <math>></math> 1 inch
 
	
 
Purpura <math>></math> 1 inch diameter
 
Spontaneous hematoma in deeper tissues
 
Joint bleeding (confirmed by aspiration, imaging study or other accepted technique)
 
	
 
Any bleeding requiring RBC transfusion over routine transfusion needs**
 

Gastrointestinal	
 
Positive stool occult blood test
 
	
 
Melanotic stool
 
Hematochezia – visible red blood mixed in stool, not requiring a transfusion
 
Hematemesis – Grossly visible blood in emesis or in nasogastric drainage tube (not related or secondary to swallowed blood)
 
	
 
Any bleeding requiring RBC transfusion over routine transfusion needs**
 

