Hemodynamic Instability			
 
• Any bleeding associated with moderate hemodynamic instability (hypotension; <math>>30</math>mmHg fall or <math>>30\%</math> decrease in either systolic or diastolic blood pressure) and requiring RBC transfusion over routine transfusion needs**
 

* Count actual bleeding (i.e. “running out” or need for basin, Kleenex, towel, etc.) not minor bleeding
 
** Red cell transfusion must be specifically related to treatment of bleeding within 24 hours of onset of bleeding
			

For inclusion, Grade 1 subset bleeding includes epistaxis, hematuria, oral petechiae, oropharyngeal bleeding, or bleeding at invasive or other wound sites. See bolded items above.
			

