### 8.2 WHO Bleeding Severity Scores

Within multiple tables, the numbers and percentages of patients will be presented by highest WHO bleeding severity score (no bleeding/grade 0, grade 1, grade 2, grade 3, or grade 4), with "highest severity score" defined as the score associated with the most severe bleeding site (given documentation of multiple sites) for the nominal time-point of interest. This distribution of highest WHO bleeding severity scores not only will be presented by nominal time-point but also will be presented by post-baseline time-points relative to baseline time-point (to allow for assessment of shift) and by both bleeding site and time-point. Differences between patient cohorts (dose levels) in the proportion of the study population showing grade 2 or higher bleeding severity for the most severe bleeding site will be tested for statistical significance per time-point using Fisher's exact test, with results displayed in a single table. To facilitate visual examination of trends, 1 or more of the summaries described above may be presented within supplementary clustered bar charts or line chart overlays.

The numbers and percentages of patients will also be presented by grade-level change in WHO bleeding severity (-2, -1, 0, +1, +2, and +3) from baseline to post-baseline time-points for the patient's most severe bleeding site at baseline, by indication of increased bleeding severity from baseline to post-baseline time-points for the patient's most severe bleeding site at baseline, and by

indication of development of new bleeding sites from baseline to post-baseline time-points. Lastly, the details of all WHO bleeding assessments will be presented in a patient-level data listing. To facilitate, within this listing, visual examination of possible post-infusion changes in bleeding severity or number of bleeding sites as associated with protocol-defined windows for the timing of infusion relative to screening (i.e., within 24 hours [as stipulated in CSP v1.1] vs. within 4 days [as stipulated in CSP v2.0+]), the data listing will be sorted first by the screening assessment dates of patients and then, within individual patients, by assessment date.

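### SAP 8.2 can record no change when the bleed that qualified the patient stops, if another site of equal or higher baseline grade persists; the tie rule, which uses post-infusion scores, extends this to the tracked-site table

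*Protocol*

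**What the plan says.** **Entry.** Grade 1 patients enter only with a listed type of bleed. The note to Table 1 in Protocol 1.9.2 gives the list, which wound sites complete: "Only a subset of patients with Grade 1 bleeding who have either epistaxis, hematuria, oral petechiae, oropharyngeal bleeding, or bleeding at invasive". Appendix A repeats the list: "For inclusion, Grade 1 subset bleeding includes epistaxis, hematuria, oral petechiae, oropharyngeal bleeding, or bleeding at invasive or other wound sites". It bolds the qualifying entries, 5 of its 10 Grade 1 entries. The other five are skin petechiae ("Petechiae of skin"), purpura up to 1 inch, soft-tissue hematoma, positive stool occult blood and vaginal spotting. The restriction applies to Grade 1 only, so any Grade 2 entry qualifies, including purpura over 1 inch.

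**Assessment.** Protocol 1.9.3 does not limit grading to the qualifying bleed: "The location of bleeding for all bleeding sites will be assessed by WHO grade during study".

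**Analysis.** Protocol 1.16 asks for the observed score and its change from baseline ("Summaries of vital signs and clinical data including WHO bleeding scores will include the observed response and the change from baseline") but gives no rule for combining sites. SAP 8.2 supplies two:

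- The patient's score at each visit is "the score associated with the most severe bleeding site (given documentation of multiple sites) for the nominal time-point of interest". This feeds Table 14.3.3.1 (by visit), Table 14.3.3.3 (shift) and Table 14.3.3.4 (Grade 2 or higher, Fisher's exact test between cohorts).
- Tables 14.3.3.5 and 14.3.3.6 follow the site that was worst at baseline. If sites tie at baseline, SAP 8.2 compares their 1-hour scores, then their 6-hour scores and so on, and keeps the site with the higher score.

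SAP 8.2 also plans counts by site and visit (Table 14.3.3.2), new sites (Table 14.3.3.7) and a patient listing (16.2.4.1).

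**The concern.** The set of findings that can admit a Grade 1 patient is narrower than the set that can hold the patient's score at Grade 1 afterwards. If the qualifying bleed stops and a non-qualifying Grade 1 finding stays, the highest grade does not move.

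The tracked-site table ought to be the remedy, since it follows one site. In a tie, however, the site is chosen by its result after infusion, and the choice always goes to the site that improved less. Selecting what to follow by its outcome biases the recorded change towards no improvement.

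The effect of dose on the WHO score is a secondary objective in Protocol 1.8.2. The SAP bases its efficacy section on hematology and transfusions, so the WHO tables of SAP 8.2 are the only planned summaries that address this objective.

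**Working it through.** The plan states no rate, effect size or power for the WHO outcome, so there is no figure to reproduce. The check applies the SAP 8.2 rules to constructed patients and then sizes the effect under stated assumptions.

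**Step 1. Count of Grade 1 entries (Appendix A).** Oral and nasal 3 (all bolded); skin and soft tissue 3 (none); gastrointestinal 1 (none); genitourinary 2 (one bolded); invasive sites 1 (bolded). Total 3 + 3 + 1 + 2 + 1 = 10, of which 3 + 1 + 1 = 5 are bolded.

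**Step 2. The rules applied, baseline to 24 h.** In each patient the epistaxis stops by 1 h and any skin sign persists unchanged.

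| Patient | Highest grade | Site tracked | Tracked change | Grade 2 or higher |
|---|---|---|---|---|
| A: Grade 1 epistaxis, Grade 1 skin petechiae | 1 to 1 (0) | skin, by tie rule | 0 | no to no |
| B: Grade 2 epistaxis, Grade 1 skin petechiae | 2 to 1 (-1) | nose | -2 | yes to no |
| C: Grade 2 epistaxis, Grade 2 purpura | 2 to 2 (0) | skin, by tie rule | 0 | yes to yes |
| D: Grade 1 epistaxis, Grade 2 purpura | 2 to 2 (0) | skin, higher at baseline | 0 | yes to yes |
| E: Grade 1 epistaxis, no skin sign | 1 to 0 (-1) | nose | -1 | no to no |

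Masking is complete in A, C and D, where the persisting site is tied or higher. In B only the highest-grade display is affected, reading -1 instead of -2. In C and D the purpura is Grade 2 and so qualifies in its own right; the epistaxis is lost from view, but the table does follow a qualifying bleed. A is the clear failure, because the site followed could not have admitted the patient.

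Table 14.3.3.6 counts increases only, so it could not show a resolution in any case. Table 14.3.3.2 would show the nasal score falling in A to D, but as counts by site and visit that do not link a patient's qualifying bleed to its later state.

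**Step 3. Size, under assumptions.** Take a cohort of 8, all Grade 1 entrants. Let p be the share whose qualifying bleed stops and q the share with a tied Grade 1 sign that persists, independent of p. Neither is in the documents. Expected number showing improvement = 8 x p x (1 - q):

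| p | q = 0 | q = 0.25 | q = 0.50 | q = 0.75 |
|---|---|---|---|---|
| 0.50 | 4.0 | 3.0 | 2.0 | 1.0 |
| 0.75 | 6.0 | 4.5 | 3.0 | 1.5 |
| 1.00 | 8.0 | 6.0 | 4.0 | 2.0 |

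For p = 0.75, the binomial chance that at least 4 of 8 show improvement, with probability p(1 - q) = 0.75, 0.5625, 0.375 or 0.1875, is 0.97, 0.76, 0.35 or 0.05.

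If only a share w of the cohort entered with Grade 1, and Grade 2 ties are ignored, the number lost from the tracked-site table is 8 x w x p x q. With p = 0.75 and q = 0.50 this is 3.0 for w = 1 and 1.5 for w = 0.5.

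**The case against.** **The SAP treats these as safety tables.** SAP 2.2.1 and section 8 place WHO scores under safety, and section 11 declares that the secondary objective was rephrased. For safety, the highest grade over all sites is suitable, and a tie rule that favours the worse site catches worsening. This stands, and is why those displays should be kept. It does not settle the matter: Protocol 1.8.2 keeps the WHO effect as a secondary objective, Protocol 1.9.9 asks for it to be described, and no other planned table does so.

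**The information is not lost.** Listing 16.2.4.1 shows every site for every patient, and 24 patients can be read by eye. This also stands, but a listing gives no summary by dose.

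A reader might infer more than the documents support:

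- *That Grade 1 skin signs hide the stopping of Grade 2 bleeds as well.* They do not. Patient B is tracked correctly at -2.
- *That the comparison between doses is diluted.* The only between-cohort WHO test uses Grade 2 or higher, which Grade 1 signs cannot affect. The SAP plans no test of resolution to Grade 0 between cohorts.
- *That the protocol admits only actively bleeding lesions and dismisses the rest.* Oral petechiae are on the list, the protocol gives no reason for the subset, and active is defined by time: "Active bleeding is defined as to occur within 4 days of infusion".
- *That non-qualifying Grade 1 findings should be scored 0.* That would record a treated Grade 2 bleed continuing at a lower grade as resolved: melanotic stool falling to occult blood, large purpura shrinking to small, vaginal bleeding falling to spotting. In an open-label trial without a control group, that error favours the product. It would also leave the tie rule in place for two qualifying bleeds, such as epistaxis and microscopic hematuria.

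**Conclusion.** The concern holds in a limited form. When another site has an equal or higher grade at baseline and persists, the highest-grade and shift tables, and the tracked-site change table, can record no change although the qualifying bleed has stopped. The firmest part is the tie rule, which selects the tracked site by its post-infusion result and so fails for a Grade 1 entrant with a tied non-qualifying finding. That follows from the written rules and needs no assumption.

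The size does rest on assumptions. The documents do not give the prevalence of coexisting findings, the share of Grade 1 entrants or the resolution rate. The illustration (6.0 expected improvements falling to 4.5, 3.0 or 1.5 of 8 at p = 0.75) takes an all-Grade-1 cohort and independence between the two sites. The loss is smaller with fewer Grade 1 entrants, if Grade 2 ties are left out.

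**What to change.** In SAP 8.2:

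1. Add a version of Table 14.3.3.5 that follows the bleed or bleeds that qualified the patient at baseline (a bolded Grade 1 entry of Appendix A, or any Grade 2 entry), each at its own site. Keep a residual lower grade at that site as scored; do not set it to 0. Patient A then reads -1, and B still reads -2.
2. Settle baseline ties from baseline information only: the qualifying bleed first and, if sites are still tied, either report every tied site or use a fixed site order stated in advance. Do not use post-infusion scores. If every site is reported, patient C shows -2 at the nose and 0 at the skin.
3. Name this table as the one that describes the effect on bleeding under Protocol 1.8.2. Keep the highest grade over all sites and the new-site table as the safety display. A tied site that worsens would still raise the highest grade and so appear in Table 14.3.3.3.

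The cost is SAP wording and one more table. Bleed type is needed as well as site where one row mixes qualifying and non-qualifying entries, as the genitourinary row does at Grade 1. The SAP should also say where other wound sites are coded, because the invasive-sites row of Appendix A names only venipuncture, line and catheter sites. The case report form is not among the documents, so whether it records bleed type needs checking.

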### **1.9.2.1 All Cohorts**

Informed consent will be obtained from thrombocytopenic (platelet count  $\geq$  5,000/  $\mu$ L and  $\leq$  70,000 per  $\mu$ L) patients who are actively bleeding or are at risk of active bleeding within the 4 weeks of initial screening. Patients are eligible who have had a documented bleeding episode(s) within the previous 4 days of screening. If they pass screening, they will be enrolled and infused. Patients who are not actively bleeding, but who are at risk for active bleeding based on medical history and prognosis (projected clinical course) within 4 weeks from their initial screening, will be monitored for active bleeding. If the patient was not actively bleeding at the time of screening, but bleeding occurs within 4 days (+ 6 hours) of initial screening, the patient does not need to be rescreened, but must have a WHO bleeding assessment and a CBC at baseline. If the patient was not actively bleeding at the time of screening, but bleeding occurs greater than 4 days and within 4 weeks of initial screening, the patient will be rescreened, enrolled and infused. Patients who are not infused within 4 weeks of initial screening are withdrawn from study. Patients who were withdrawn from study may be re-entered into study if they were: 1) previously not infused with Thrombosomes, and 2) meet all the enrollment requirements of study. All enrolled patients will be assigned to cohorts based on order of enrollment and timing of infusion of Thrombosomes.

All enrolled patients with active bleeding of modified WHO Grade 1 (subset of patients with either epistaxis, hematuria, oral petechiae, oropharyngeal bleeding, or bleeding at invasive or other wound sites) or Grade 2 bleeding will receive Thrombosomes. Grades 0, 3, or 4 bleeding are not inclusion criteria for enrollment. Active bleeding is defined as to occur within 4 days of infusion. If the patient progresses to grade 3 or 4 bleeding during that time, they will be excluded from the study and will not be infused. Doses will be adjusted per weight of each patient. The starting dose for patients in Cohort 1 will be approximately 5 ml of Thrombosomes or approximately  $9.45 \times 10^7$  particles/kg or 165 TGPU per kg by IV infusion. The dose for patients in Cohort 2 will be approximately 10 ml of Thrombosomes or approximately  $1.89 \times 10^8$  particles/kg or 330 TGPU per kg by IV infusion. The dose for patients in Cohort 3 will be one dose of approximately 20 ml of Thrombosomes or approximately  $3.78 \times 10^8$  particles/kg or 660 TGPU per kg by IV infusion. See Table 2.

Pre-infusion, infusion (Day 1), and post-infusion follow up through Day 30 (+2 days) will be performed as outlined in *Table 4* below. Patients require observation at a minimum through the completion of Visit 4 (6 hours post-infusion). Patients may be admitted and observed overnight at the discretion of the PI. If the subject is an in-patient on Days 3-5, he/she should be assessed and samples collected as described in Table 4.

All patients in each cohort will be evaluated for any signs of AEs, serious adverse events (SAEs) and serious adverse drug reactions (SADRs) after infusion.

Patient infusions cannot occur on the same day. Once an enrolled patient has been infused, he/she must reach Day 4 without a suspension or stopping rule (1.9.8 Stopping Rules and Procedures for Study) event being reported prior to a subsequent patient being infused. In addition, there will be at least a two-week interval between cohorts to allow an independent Data Monitoring Committee (DMC) to review all patients' accumulated safety data after visit Day 6 from Cohort 1 and then again after the last patient from Cohort 2 has completed visit Day 6 in order to recommend whether the study should advance to the next cohort. Refer to Appendix B- Flow Diagram of Study Events.

